# Clinical Investigation Plan (CIP)

Study Name: VivaSight-DL study (CIS-009)  
 Ethical committee number: S-20180081

CLI-000427

Rev. 02

normalize the data. If the observations are still not normally distributed, a Mann-Whitney U test will be used.

## Tertiary end-points

- Qualitative measures (questions to the patient)
  - Any side effects from the surgery: Data will be summarized using frequency tables and examined via regression model as suitable.
  - Daily function level prior surgeryPostoperative scores will be summarized in a frequency table and examined via regression model as suitable.
- Qualitative measures (questions to the person who intubated)
  - Ease of tube placement (on a scale from 1=very easy to 5=very difficult)
  - How would you rate the overall perception of quality and functionality of the tube (DLT or VivaSight)? (Very poor, poor, acceptable, good, very good)
  - Would you prefer to use this method for single lung ventilation in the future? (yes/no)

A Chi-sqaure test will be applied to examine whether qualitative measures are significantly different for procedures using VivaSight-DLT compared to a conventional DLT.

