## Tertiary end-points:

- Qualitative measures (questions to the subject) (appendix V)
  - Any side effects from the surgery
  - Daily function level prior surgery
- Qualitative measures (questions to the person who intubates) (appendix VI)
  - Ease of tube placement (very easy, easy, acceptable, difficult, very difficult)
  - How would you rate the overall perception of quality and functionality of the tube (VivaSight-DL or conventional DLT)? (Very poor, poor, acceptable, good, very good)
  - Would you prefer to use VivaSight-DL or conventional DLT in the future (VivaSight-DL/conventional DLT)

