### 7.9 Awakening of subject and follow up

Immediately after the surgery, the physician is asked to complete a questionnaire regarding the procedure just performed (Appendix VI).

All subjects are woken up immediately after surgery. Within forty-eight hours after the surgery, the subject will be contacted (in the hospital room or over the phone) by a research assistant who will ask questions regarding the subject's health-related life quality and potential side effects from the intubation (Appendix V). It will be the same research assistant who contacts all subjects in order to ensure identical data collection across subjects.

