## APPENDIX VI: QUESTIONNAIRE FOR SUBJECTS

### Spørgeskema omhandlende helbredsrelateret livskvalitet og bivirkninger efter operation i hjerte-lunge området

I forbindelse med at De har deltaget i et forskningsstudie og har fået foretaget en operation med behov sikring af dine luftvejene på Odense universitetshospital, vil vi bede Dem besvare nedenstående spørgeskema omhandlende din generelle helbredsrelaterede livskvalitet samt eventuelle bivirkninger efter din operation.

Forsøgsperson nummer: \_\_\_\_\_

Dato for udfyldelse: \_\_\_\_\_

Tidspunkt for udfyldelse: \_\_\_\_\_

Spørgsmål omhandlende helbredsrelaterede livskvalitet						Kommentarer
Hvordan vil De vurdere Deres overordnet livskvalitet indenfor de sidste 4 uger?	 Dårlig	 Mindre god	 God	 Meget god	 Fremragende	
I hvor høj grad har De haft smerter indenfor de sidste 4 uger?	 Slet ikke	 I mindre grad	 I nogen grad	 I høj grad	 I meget høj grad	
I hvor høj grad har Deres smerter påvirket Deres hverdag?	 Slet ikke	 I mindre grad	 I nogen grad	 I høj grad	 I meget høj grad	
I hvor høj grad har De følt dem ængstelig eller deprimeret indenfor de sidste 4 uger?	 Slet ikke	 I mindre grad	 I nogen grad	 I høj grad	 I meget høj grad	
Hvordan vil De vurdere Deres helbred alt i alt?	 Dårligt	 Mindre godt	 Godt	 Meget godt	 Fremragende	
Spørgsmål omhandlende eventuelle bivirkninger efter operationen						Kommentarer
Hvor mange timer er der gået siden Deres operation?	 0-4	 5-9	 10-14	 15-19	 Over 20	
Har De tidligere fået foretaget en lignende operation?	 Ja	 Nej				
Har De oplevet hoste efter Deres operation?	 Ja	 Nej				

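### A function measure labelled as pre-surgical is a tertiary end-point but is asked only after surgery, so an arm difference in it cannot be read as a device effect

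*Combined protocol and SAP*

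**What the plan says.** Section 4 includes among the tertiary end-points, as a question to the subject, "Daily function level prior surgery". Section 18.3.3 repeats the item with its analysis: "Daily function level prior surgeryPostoperative scores will be summarized in a frequency table and examined via regression model as suitable". The two patient items and three physician items in that section share the label of qualitative measures, and the list closes with: "A Chi-sqaure test will be applied to examine whether qualitative measures are significantly different for procedures using VivaSight-DLT compared to a conventional DLT".

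On timing, section 7.9 states: "Within forty-eight hours after the surgery, the subject will be contacted (in the hospital room or over the phone) by a research assistant". The contact covers "questions regarding the subject's health-related life quality and potential side effects from the intubation", and section 5.1 also places the questionnaire after surgery. The data collected at recruitment (section 7.2) are age, sex, height, weight, ASA class, indication, enrolment date and eligibility. No function or quality-of-life measure is among them.

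The questionnaire is in Danish, in Appendix VI (the body text cites it under other appendix numbers). Its first block has five quality-of-life items. The first reads "Hvordan vil De vurdere Deres overordnet livskvalitet indenfor de sidste 4 uger", a 4-week look-back. Section 18.3.4 sets a two-sided 5% level and a Bonferroni correction for exploratory analyses, without giving the number of tests or the family.

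**The concern.** Under sections 5.4 and 7.3 the envelope is opened before the tube is used. The tube cannot change how a patient functioned before the operation, so comparing the arms on that state cannot show a treatment effect. Even so, the item is listed as an end-point and is to be modelled and apparently tested.

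The timing adds a second problem. Patients are asked about their recent weeks within two days of thoracic surgery, when pain and recovery may colour the answers. The analysis line describes the same item both as prior to surgery and as postoperative, so the reader cannot tell which state is meant. At stake is a tertiary result that invites a device interpretation it cannot bear, and the loss of a usable baseline description in a trial of 50 patients.

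**Working it through.** The plan gives no figure for this end-point. Its one calculation is for the primary outcome: (0.23622 + 0.01087) × (1.96 + 1.28)² / (0.37234 − 0.01087)² = 19.852 per arm, so 40 in total, and 40 / (1 − 0.20) = 50. That reproduces and does not depend on anything below.

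**Step 1: what each item refers to (Appendix VI).**

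| Item | Time window in the wording |
|---|---|
| Overall quality of life | last 4 weeks |
| Pain | last 4 weeks |
| Effect of pain on everyday life | none stated |
| Anxiety or depression | last 4 weeks |
| Overall health | none stated |

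Three of five look back 4 weeks and two have no window. None is worded to refer to the time before the operation.

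**Step 2: how much of the window follows surgery.** Contact is within 48 hours, so at most 2 of 28 days: 2/28 = 7.1%. At least 26/28 = 92.9% of the window precedes the operation. This is a share of calendar time. It does not bound how strongly the last two days influence an answer.

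**Step 3: set the two possible purposes side by side.**

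- As a baseline: the answers come after randomisation, after the tube and after surgery, so they are not protected from any of these.
- As a post-operative outcome: about 93% of the 4-week window lies before the tube could act, so any real effect is diluted, and the two items without a window have no defined period.

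**Step 4: false positives if the items were purely pre-surgical.** Every null hypothesis of no arm difference would then be true by randomisation.

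- One item tested at 5%: 5%.
- Five independent tests at 5%, uncorrected: 1 − 0.95⁵ = 0.226, about 23%. Positive correlation between the items would lower this.
- Five independent tests with Bonferroni over five (1% each): 1 − 0.99⁵ = 0.049, about 4.9%.

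As a check on the nominal 5%, a simulated five-level chi-square test with 20 to 25 patients per arm and no true difference rejected in 3.7% to 4.8% of 20,000 trials per setting. The category shares were assumed: equal, or 5/15/40/30/10%. The test is thus at or slightly below its nominal level, so 23% is if anything a little high.

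**The case against.** The chi-square sentence may not cover this item. Both patient items already have a method (frequency table and regression), the three physician items have none, and the sentence directly follows the physician list. That reading is possible. The shared label makes the wider reading the more natural one, and nothing exempts the patient items. Even on the narrow reading, the item stays an end-point with a regression whose role for it, outcome or covariate, is not stated.

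A reader might infer that any arm difference here must be chance or recall bias. The documents do not support that. Two items have no window and the others can include up to two post-operative days, so a real post-operative effect could enter the answers. Sections 6.4 and 18.3.2 also replace withdrawn subjects and exclude early dropouts, so selection after randomisation is another possible source of difference.

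A reader might also take 23% as the plan's error rate. That ignores the Bonferroni rule in section 18.3.4 and assumes that all five items represent daily function. No document makes that link, and only the item on pain in everyday life refers to it directly.

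The run-together words in the analysis line may be a lost separator from PDF extraction, and postoperative may mean only that the scores are collected after surgery. Nothing is rested on the missing break. Finally, this is a tertiary measure with no pass/fail criterion (section 18.5) and is not among the effect measures of the cost-effectiveness model (section 18.7). Nothing says that a difference would be reported as a device effect. That limits the consequence but does not make the result interpretable.

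**Conclusion.** The point holds in a limited form. A mainly pre-surgical measure is listed as an end-point, is asked only after surgery, and is to be modelled and apparently compared between arms. A difference could reflect chance, recall, recovery from surgery, post-randomisation selection or a small true post-operative effect, and the data cannot separate these. It therefore cannot be read as a device effect.

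The false-positive cost lies between 5% (one item) and about 23% (five independent, uncorrected tests), and is about 4.9% if Bonferroni is applied over the five. These figures assume purely pre-surgical items. Bonferroni limits false positives but does not give a pre-surgical difference a meaning, and uninformative tests in the family would tighten the threshold for the useful ones. The primary outcome, the sample size and the listed effect measures of the economic model are untouched. This is a worthwhile minor correction, not a threat to the trial's main conclusion.

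**What to change.** Ask the five quality-of-life items at the pre-operative visit in section 7.2, before the envelope is opened. Report them by arm as baseline characteristics with no between-arm test. Remove the item from the tertiary end-points in section 4, and in section 18.3.3 remove its regression line and state that the chi-square sentence does not cover it. Keep the cough, hoarseness and throat-pain items in the 48-hour contact. In section 18.3.4, state which tests the Bonferroni correction covers and how many there are.

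If the sponsor wants a post-operative quality-of-life outcome, define it separately, with items that carry an explicit post-surgery window.

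The cost is modest: one short form split over two existing contacts, and an amendment submitted to the Ethics Committee (section 20.2). There are two practical drawbacks. Section 7.9 uses a single research assistant for consistency, whereas section 7.2 data are taken by whichever investigator obtained consent. Some forms will also come from patients later excluded because an experienced physician was assigned (sections 7.3 and 12.2).

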### 18.3.4 Level of significance and handling of multiplicity

All statistical tests will be two-sided and will be performed at the significance level ( $\alpha$ ) of 5%. To account for the explorative analysis', a Bonferroni correction is used.

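### Two five-level ordered physician ratings are compared with an unordered chi-square test; a rank or proportional-odds analysis would usually be more powerful and would give a directional estimate

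*Combined protocol and SAP*

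**What the plan says.** Section 18.3.3 lists three items for the person who intubates:

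- ease of placement: "Ease of tube placement (on a scale from 1=very easy to 5=very difficult";
- overall quality and functionality, with levels "Very poor, poor, acceptable, good, very good";
- future preference: "Would you prefer to use this method for single lung ventilation in the future? (yes/no".

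It then gives one method: "A Chi-sqaure test will be applied to examine whether qualitative measures are significantly different" between the two tubes. Section 4 has the same ordered format for ease: "Ease of tube placement (very easy, easy, acceptable, difficult, very difficult". No trend test, rank test, ordinal model, exact test or small-count rule is named for these items.

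For the numeric secondary outcomes, the same section falls back on a Mann-Whitney U test when data are not normal. For the subject items it gives frequency tables and a regression model where suitable. Section 18.3.4 adds: "All statistical tests will be two-sided and will be performed at the significance level" of 5%, and "To account for the explorative analysis', a Bonferroni correction is used". The number of tests in that correction is not stated.

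**The concern.** The question behind both ratings is directional: is one tube easier to place, or better rated, than the other? A chi-square test on a 2x5 table asks only whether the two distributions differ in any way. It spends 4 degrees of freedom and gives the same answer if the five columns are shuffled. A significant result would not say which tube did better, and a consistent shift along the scale is less likely to be detected than with a test that uses the order. With 50 ratings in 10 cells, the usual expected-count condition is also hard to meet. At stake is how informative the usability comparison is; no primary conclusion depends on it.

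**Working it through.** **1. The plan's own sample size (Section 18.1, primary outcome only).** n per arm = (0.23622 + 0.01087) × (1.96 + 1.28)² / (0.37234 − 0.01087)² = 0.24709 × 10.4976 / 0.13066 = 19.85. So N = 39.70, rounded to 40, and 40 / 0.80 = 50. The figure reproduces. No power figure exists for the physician ratings.

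**2. Order is ignored.** Let a_j and b_j be the counts at level j in the two equal arms. Each expected count is (a_j + b_j)/2, so

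X² = Σ (a_j − b_j)² / (a_j + b_j), on 4 degrees of freedom.

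This is a plain sum over levels, so relabelling or reordering them leaves it unchanged. The Wilcoxon statistic W = Σ a_j r_j, with r_j the midrank of level j, does use the order.

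**3. Expected counts.** The mean expected count is 50 / 10 = 5. Each expected cell is half its column total, so unless every level is used exactly 10 times, at least one column total is below 10 and at least two cells are below 5. For example, an assumed distribution of 10/20/40/20/10% in both arms gives 2.5, 5, 10, 5 and 2.5 per arm, with 4 of 10 cells below 5 before any sampling variation.

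In simulation, the average share of expected cells below 5 is 44–65% at 25 per arm over five levels. It is about 57–73% at 20 per arm (the planned 20% dropout) and 25–31% if only three levels are used.

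**4. Type I error.** Simulated chi-square size at nominal 0.05 and 25 per arm is 0.030–0.048. The test is mildly conservative when ratings are skewed; it is not inflated.

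**5. Power.** Inputs from the documents: 25 per arm (Section 5.1), 1:1 allocation (Section 5.4), two-sided 5% (Section 18.3.4). Assumed, because the documents give nothing: the control distribution and a proportional-odds shift, logit P(Y ≤ j | test) = logit P(Y ≤ j | control) + ln(OR). There were 20,000 simulated trials per scenario. Seven control distributions (uniform, symmetric, skewed) were used; the rows for OR 1.5 and 10 use four of them.

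| OR | Chi-square | Wilcoxon | Loss (points) |
|---|---|---|---|
| 1.5 | 0.06–0.08 | about 0.12 | 4–6 |
| 2 | 0.11–0.15 | 0.22–0.27 | 11–13 |
| 3 | 0.26–0.34 | 0.46–0.57 | 20–23 |
| 4 | 0.39–0.52 | 0.62–0.76 | 23–25 |
| 6 | 0.59–0.76 | 0.81–0.93 | 16–22 |
| 10 | 0.90–0.94 | 0.98–0.99 | 5–8 |

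**6. Sensitivity.**

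- Three levels used (40/40/20%): 0.184 v 0.244 at OR 2, 0.397 v 0.497 at OR 3 and 0.575 v 0.684 at OR 4, a loss of 6–11 points.
- Bonferroni with an assumed 3 tests (alpha 0.0167): loss 8–9 points at OR 2 and 19–27 at OR 3–4.
- Bonferroni with an assumed 14 tests (alpha 0.0036): loss 12–13 points at OR 3 and up to 32 at OR 6.
- Non-monotone difference (10/20/40/20/10% v 25/20/10/20/25%): chi-square 0.60 v Wilcoxon 0.06, so the ranking reverses.

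**The case against.** The strongest reply is that little depends on these items. They are tertiary, Section 18.5 sets no pass/fail criterion for them, and they enter neither the sample size nor the effect measures of the cost-effectiveness model in Section 18.7. The better test is itself weak here: at an odds ratio of 2 the Wilcoxon has only 0.22–0.27 power, so moderate differences would often be missed either way. All of this stands, and it keeps the point minor.

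Chi-square also does better when ratings move towards both extremes or otherwise change non-monotonically. That stands as the one real trade-off, but a shift towards easier or better is the natural question for these scales.

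Two limits apply to any test chosen. Nothing restricts a physician to one subject, so ratings may cluster by physician, and both tests assume independence. Appendix VII also prints the quality item with difficulty options in place of the poor-to-good levels in Section 18.3.3; a better test does not repair that mismatch.

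A reader might infer three stronger claims that the documents do not support:

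- *That sparse cells make the p-value misleading.* Simulated size stays at 0.030–0.048, so the false-positive rate is controlled.
- *That a loss of 20–25 points is a property of the plan.* At 5% it applies near odds ratios of 3 to 4 under assumed distributions.
- *That side-effect severity has the same fault.* Section 18.3.3 already allows a regression model for the subject items. The shared label of qualitative measures leaves the reach of the chi-square sentence somewhat unclear, but not enough to carry that claim.

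**Conclusion.** The point holds for the two five-level physician ratings and no further. That the test ignores order follows from its form. That roughly half the expected cells fall below 5 follows from 25 per arm, provided all five levels are used. The size of the power loss is conditional on a consistent proportional-odds shift and on rating distributions that the documents do not supply. At 5% it runs from about 4 to 25 points, largest near odds ratios of 3 to 4 and smaller if raters use only three levels. It changes under the Bonferroni correction by an amount that cannot be fixed while the number of tests is unstated. The absence of a directional estimate does not depend on those assumptions.

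**What to change.** In Section 18.3.3, for ease of placement and for overall quality and functionality, replace the chi-square test with one of:

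- a tie-corrected Wilcoxon (Mann-Whitney) test, already the fallback for the secondary outcomes; or
- a proportional-odds model reporting the odds ratio and 95% CI, which also supplies the directional estimate.

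Keep chi-square for the yes/no preference item, and add Fisher's exact test when an expected count is below 5. Continue to show the full frequency table for each rating so that a non-monotone pattern is visible.

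The change costs wording and analysis code only: no further subjects or data. The price is lower power against non-monotone differences.

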### 18.3.4 Level of significance and handling of multiplicity

All statistical tests will be two-sided and will be performed at the significance level ( $\alpha$ ) of 5%. To account for the explorative analysis', a Bonferroni correction is used.

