## 18. DATA MANAGEMENT AND STATISTICAL ANALYSIS

### 18.1 Sample size

The following formula is used to validate that the chosen sample size is sufficient to detect an effect on the primary outcome):

$$n_1 \geq \left( \frac{(\sigma_{DLT}^2 + \sigma_{vivasight}^2) * (\lambda_z + \lambda_\beta)^2}{(\bar{x}_{DLT} - \bar{x}_{Vivasight})^2} \right)$$

Combined standard deviation and grand mean are based on three studies (2,12,13).

$$\begin{aligned} \bar{x}_{DLT} &= 0,37234 \text{ bronchoscopes used to correct DLT placement} \\ \bar{x}_{vivasight} &= 0,01087 \text{ bronchoscopes used to correct vDLT placement} \\ \sigma_{DLT}^2 &= 0,23622 \text{ bronchoscopes} \\ \sigma_{vivasight}^2 &= 0,01087 \text{ bronchoscopes} \end{aligned}$$

We set power to 90% thus the  $\lambda_\beta = 1.28$  and significance level at 5%  $\rightarrow \frac{0.05}{2} = 0,025 \rightarrow \lambda_z = 1,96$

Thereby, to reject the  $H_0$  the sample size must be:

$$\begin{aligned} n_1 &\geq \left( \frac{(0,23622 + 0,01087) * (1,96 + 1,28)^2}{(0,37234 - 0,01087)^2} \right) = 19,852 \text{ patients} \\ N &= 19,852 * 2 = 39,7035 \rightarrow 40 \text{ patients} \end{aligned}$$

Therefore, a total sample size (N) of 40 generates a power of 90%. A sample size of 50 patients allows a potential dropout rate of 20 percent.

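### Section 18.3.4 applies Bonferroni to a set of tests that it never identifies, so the threshold for the nine tested secondary outcomes and the tertiary tests is left open

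*Combined protocol and SAP*

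**What the plan says.** Section 18.3.4 is the whole multiplicity plan and has two sentences. The first covers everything: "All statistical tests will be two-sided and will be performed at the significance level" of 5%. The second reads: "To account for the explorative analysis', a Bonferroni correction is used".

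Elsewhere the endpoints are called primary, secondary and tertiary (sections 4 and 18.3.3). Section 18.3.3 plans:

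- one test of the primary outcome;
- a t-test or Mann-Whitney test for each of nine secondary outcomes;
- a chi-square test for the qualitative measures, with regression where suitable for the patient items. Five tertiary items are listed.

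Section 18.1 sizes the trial on the primary outcome only, with the error rate set by "and significance level at 5"% two-sided, and concludes that "a total sample size (N) of 40 generates a power of 90"%.

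**The concern.** A Bonferroni correction is defined by its family and its divisor, and the plan gives neither. The one word that should identify the family matches no heading or endpoint in the document. At least two readings leave the primary alone and still fit the text: correct the tertiary tests only, or correct secondary and tertiary tests together. They give different answers for the same result. A secondary p-value of 0.02 is significant on the first reading and not on the second.

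Nothing fixes the choice before the data are seen. The two tubes are visibly different, no masking is described, and the sponsor analyses the data internally (section 18.2). Because either reading can be called compliant with the plan, choosing one later need not be reported as a deviation under section 18.4. What is at stake is the credibility of the secondary and tertiary claims.

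**Working it through.** **1. The plan's own figure.** Inputs from section 18.1: variances 0.23622 and 0.01087 (sum 0.24709); means 0.37234 and 0.01087 (difference 0.36147); multipliers 1.96 and 1.28.

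n per arm = 0.24709 × (1.96 + 1.28)² / 0.36147² = 0.24709 × 10.4976 / 0.13066 = 19.85, so 20 per arm and N = 40.

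Power at 20 per arm = Φ(0.36147 / √(0.24709/20) − 1.96) = Φ(3.252 − 1.960) = 90.2%. Allowing 20% dropout, 40 / 0.8 = 50. The figures reproduce at an uncorrected two-sided 5%, so section 18.1 treats the primary as a single test at that level. This agrees with the first sentence of section 18.3.4.

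**2. Counting the other tests.** Section 4 lists ten secondary endpoints. Section 18.3.3 gives a test for nine; the number of times the backup anesthesiologist is called has none. The count of nine includes the restriction outcome, which section 4 grades on three levels and section 18.3.3 treats as a count of surgeon stops. With the five listed tertiary items there are 9 + 5 = 14 non-primary items.

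**3. What the choice of reading changes.** For k independent tests at 5%, the chance of at least one false positive is 1 − 0.95^k. The Bonferroni threshold is 0.05/k.

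| Family | k | Chance if uncorrected | Bonferroni threshold |
|---|---|---|---|
| Tertiary items only | 5 | 23% | 0.0100 |
| Tested secondary outcomes | 9 | 37% | 0.0056 |
| Ten secondary endpoints, if the call count gets a test | 10 | 40% | 0.0050 |
| Nine secondary plus five tertiary | 14 | 51% | 0.0036 |

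Independence is for illustration only. Repositioning counts, repositioning time, surgeon stops and backup time are plainly related.

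**4. Holm against Bonferroni.** Holm compares the smallest of nine p-values with 0.05/9 = 0.0056, the next with 0.05/8 = 0.00625, and so on up to 0.05, stopping at the first failure. Its first step is the Bonferroni threshold and each later one is looser, so it rejects everything that Bonferroni rejects. It controls the family-wise error rate at 5% whatever the correlation between tests.

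To illustrate the gain, take nine independent tests in which each true effect has 80% power at an uncorrected 5%. Average power per true effect under Bonferroni is Φ((1.960 + 0.842) − 2.773) = 0.51. By simulation, Holm gives about 0.53 with three true effects and 0.60 with eight.

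**The case against.** The best defence is that the intended meaning can be guessed. Explorative may simply mean every test that is not primary, and section 18.3.3 plans such tests, so only the label is missing. The 5% in the first sentence may be the level before division. On that reading the primary keeps 5%, the remaining tests are corrected, and the plan needs only clarification. Much of this stands: the set of non-primary tests is not empty, and Bonferroni on a named family is valid. What does not stand is that the text settles the matter. It supports a tertiary-only correction equally well, and it gives no divisor under either reading.

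A reader might also infer something stronger: that the primary significance level is contradictory and the 90% power is at risk. If the primary shared a correction with the nine secondary tests (k = 10, level 0.005), power by the section 18.1 approximation would be Φ(3.252 − 2.807) = 67% at 20 per arm and Φ(3.636 − 2.807) = 80% at 25. With the five tertiary items as well (k = 15, level 0.0033), it would be Φ(3.252 − 2.935) = 62% and Φ(3.636 − 2.935) = 76%. The documents do not support that reading. Sections 18.1 and 18.3.4 both give 5% two-sided, the correction is tied to explorative analyses, and no passage places the primary in the corrected set. These figures rest on divisors that the plan never states, and they show only why one sentence excluding the primary is worth adding.

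**Conclusion.** The point holds for the non-primary tests. The correction cannot be carried out as pre-specified, because its family and divisor are missing and the sentence before it sets every test at 5%. For the nine tested secondary outcomes, the open range runs from an uncorrected 5%, with about a 37% chance of at least one false positive under illustrative independence, to a threshold of 0.0056 if they alone form the family, or 0.0036 if the five tertiary items join them. The true family-wise figure depends on correlations that the documents do not give.

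The primary analysis is not affected on the natural reading: one test at two-sided 5%, with the stated sample size and power reproduced at that level.

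**What to change.** Rewrite section 18.3.4 so that it:

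- states that the primary outcome is tested alone at two-sided 5% and lies outside any multiplicity correction;
- lists the non-primary tests in the corrected family and gives their number. This means deciding whether the backup-call count, an endpoint in section 4 with no test in section 18.3.3, gets a test (family of ten secondary tests) or is only described (family of nine);
- limits the 5% sentence to the primary outcome and to any test declared outside the family;
- replaces Bonferroni with the Holm procedure at 5% within that family;
- says in advance whether the tertiary tests are inside or outside the family. Their planned analyses can otherwise stay as they are.

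Suitable wording: *The primary outcome is tested alone at two-sided 5%. The following secondary outcomes [list, number] form one family, tested by the Holm procedure at a family-wise two-sided 5%. The tertiary tests are [inside / outside] this family.*

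The cost is a revision of the statistical section, with no extra patients or data. Against Bonferroni on the same family, Holm loses no rejections. Matching simultaneous confidence intervals are less simple under Holm, but the plan promises only ordinary 95% intervals. Against uncorrected 5% testing, secondary claims face a stricter bar, which the existing Bonferroni sentence already implies for whatever it covers.
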